## SUMMARY

**Rationale:** From 2015-2020, the 'Healthy Primary School of the Future' intervention took place in Parkstad. The school environment of four primary schools changed. Two schools became 'Healthy Primary Schools of the Future'; providing their students with a healthy lunch and structured physical activity (PA) sessions during lunch time breaks. Two other 'Physical Activity Schools' only implemented the structured PA sessions. METC Z previously decided that this study falls under non-WMO guidelines (METC-Z no. 14-N-142). Interim analyses showed promising effects of the intervention; at two-year-follow-up, the study showed a significant decrease in BMI z-score of children in the 'Healthy Primary Schools of the Future' as compared with children in control schools. Also, positive intervention effects on dietary and PA behaviours were observed. Following these promising results, childcare centres of educational board Prisma have expressed their interest in implementing changes fitting the 'Healthy Primary School of the Future' initiative. However, this is more complex than it seems to be, as budget to implement changes is lower than in the original trial, and all childcare centres have a unique context. Therefore, there is a need to investigate how 'Healthy Primary School of the Future' can successfully be implemented in various, real-life school-settings. It is hypothesised that to maximise implementation and sustainability, each childcare centre will need to put together a set of changes and interventions which fit the context and needs of all stakeholders involved (e.g., the school board, teachers, parents and children).

**Objective:** The main objective is to study the implementation process of 'Healthy Childcare Centre of the Future' in different school-contexts and develop guidelines that can be used to facilitate widespread dissemination of the initiative. Secondary objectives include evaluating the effects of the 'Healthy Childcare Centre of the Future' on children's BMI z-score, general health, dietary and PA behaviours and school well-being. To reach these objectives, a process evaluation, effect evaluation and cost-effectiveness evaluation will be executed.

**Study design:** A non-randomised, non-controlled, observational study design.

**Study population:** Children in study years four to six (at baseline) of twelve childcare centres located in Limburg.

**Main parameters/endpoints:** The main study parameter of the effect evaluation is the change in absolute BMI z-score, which will be compared between the childcare centres that are categorised based on their degree of implementation (using categories based on the Diffusion of Innovations Theory).

**Methods:** Data will be collected in the form of questionnaires (parents, children, teachers/pedagogical employees, directors), anthropometric measurements (children), interviews (teachers/pedagogical employees, directors), observations and analyses of minutes of meetings.

**Nature and extend of the burden and risks associated with participation:** No intervention is allocated in this study other than activities planned by childcare centres in accordance with wishes and needs of childcare centre staff and parents. All outcome measures are non-invasive. The measurement protocol was designed while taking into account both a minimal burden for participants and a relevant scientific output for stakeholders (e.g., school board, teachers, parents/caregivers and children). Burden of participants is minimised by incorporating most measurements in the regular school day.

## 1. INTRODUCTION

In the Netherlands, the number of children suffering from overweight and obesity is increasing. In Peel en Maas, a region in the north of Limburg, 5.0% of 4.5-6 year-olds and 13.3% of 9-11 year-olds suffered from overweight in 2016. For obesity, these percentages were 1.8% and 2.0% respectively (1). The increasing prevalence of juvenile overweight and obesity is a public health concern, because they often have negative psychological and social consequences. Furthermore, they can increase the risk of developing certain non-communicable diseases (NCDs). The health risks associated with overweight and obesity also lead to an increase in health care costs, which puts a large economic burden on society (2-4).

Important causes of the increasing prevalence of juvenile overweight and obesity are unhealthy dietary and physical activity (PA) habits. (WHO, 2017). Despite the health benefits associated with engaging in healthy lifestyle behaviours, the present habits of Dutch children show room for improvement. Currently, only 42% of children aged 4–9 years consume at least 150 grams of fruit per day; this percentage drops to 20% for 9–12 year-olds. The prevalence of vegetable intake shows similar percentages: 41% of 4–9 year-olds and 25% of 9–12 year-olds eat at least 150 grams of vegetables per day (CBS, RIVM, & The Netherlands Nutrition Centre, 2017). Looking at PA habits, only 17.1% of Dutch children aged 4-11 reach the advised daily norm of 60 minutes of moderate to vigorous PA and only 29.9% reach the Fitnorm (i.e., 20 min three days/week exhaustive PA) (7). These numbers underpin the importance of promoting healthy lifestyle habits in young children. Doing so could not only contribute to improvements in health but also to increased well-being (i.e., better concentration, increased feelings of happiness and satisfaction).

The school setting is the ideal environment to promote healthy lifestyle habits as:

- 1) Health behaviours are learned at a young age, and healthy lifestyles learned early in life usually track into adulthood (8);
- 2) There is strong evidence that healthy lifestyles are correlated with high academic achievements (Bass, Brown, Laurson, & Coleman, 2013; Edwards, Mauch, & Winkelman, 2011; Florence, Asbridge, & Veugelers, 2008; Van Dusen, Kelder, Kohl, Ranjit, & Perry, 2011);
- 3) Children from all socio-economic classes will be reached;
- 4) Directors, teachers, parents/caregivers and children are all involved in school-based communities, thereby involving not only children, but an entire community.

Worldwide, several high-quality health-promoting school initiatives have been evaluated (13,14). According to the WHO, a health-promoting school is one that constantly strengthens its capacity as a healthy setting for living, learning and working (15). In general, a school is considered health-promoting if interventions are given to reduce risk factors for NCDs (e.g., obesity, low PA levels, smoking, unhealthy nutrition), demonstrating active participation by the school and involving health-promoting activities in all or one or two of the following areas:

- (a) the school ethos and/or environment, such as school policy;
- (b) the school curriculum;
- (c) the family and/or community.

The majority of studies on healthy school environment focus on obesity prevention (16,17). Several meta-analyses and reviews showed that school-based projects can be successful, although effects are often modest (14,16–19). In a meta-analysis which included eighteen school-based RCT intervention studies in children, significant Body Mass Index (BMI) reductions of  $-0.076$  (95% CI  $-0.123$  to  $-0.028$ ,  $p < 0.01$ ) were found in intervention vs. control schools. However, results remain modest and several school-based interventions did not show reductions in BMI (20). The effects of health-promoting schools on lifestyle behaviours such as sedentary behaviour and dietary behaviour have frequently been studied as well. Saraf et al. showed that of all school-based interventions aimed at reducing risk factors associated with NCDs, 80% reported at least some evidence of a positive intervention effect (21). Examples of nutrition-related behaviours which can be improved with school-based interventions are consumption of high-fibre foods, healthier snacks, water, milk, fruit and vegetables (22). Also breakfast skipping, eating disorders, consumption of low-nutrient dense food, fatty and cream foods and sugar-sweetened beverages can be reduced in health-promoting schools. In a meta-analysis of Evans et al. (2012), a significant average improvement of 0.25 portions (95% CI: 0.06, 0.43 portions) of fruit and vegetable daily intake (fruit juice excluded) was found after implementation of school health interventions (23). Health-promoting schools are often accompanied with high exploitation costs for personnel, meals and logistics, which is a high barrier for implementation. However, health-promoting schools have the potential to be highly cost-effective, as effects on several outcome parameters are expected. Prior studies already showed that school-based programmes may be more cost-effective in terms of quality of life and BMI when compared with other obesity prevention programmes (24,25).

Despite the potential of school-based health interventions, they are often not integrated in the school system and are characterised by relatively low priority, a lack of coordination, and are often supply-driven, resulting in limited effects or effects that diminish in the long term (26,27). A major limitation of many school-based programmes is the lack of space in already full curricula, and time and financial concerns (20). In most of the school-based programmes, the physical and social environment is not adapted towards the 'individual-level' interventions. For example, Doak et al. highlight the difference between teaching children that they should be more active and eat more fruit and vegetables, and actually giving them the opportunity in terms of time, space and facilities to do so (28). Additionally, interventions are often not context-specific, although evidence suggests that there is a strong interaction between an intervention and the context in which it is being implemented (29). This means that what works in one school might not work in other schools, and therefore interventions should be adapted towards the specific context in which they are being implemented.

The above-mentioned flaws were taken into account in the development of 'The Healthy Primary School of the Future' (HPSF). HPSF is a Dutch initiative based on the Health Promoting School Framework (including e.g., a whole school approach, high involvement of parents/caregivers and partnerships). It acknowledges that implementation challenges can occur due to an interaction between the intervention and the context (30,31). In 2015, a quasi-experimental trial aiming to evaluate HPSF was initiated. This trial was previously registered on ClinicalTrials.gov (NCT02800616). It involved eight primary schools in the South of Limburg: four intervention schools and four control schools. Intervention schools introduced changes regarding the following key elements:

- **A healthy school lunch**, which children consume together. The lunch is provided by school or an external caterer and its contents are in accordance with the guidelines from the Netherlands Nutrition Centre (at least 80% of the products being served are from the Wheel of Five);
- **A longer lunch break** of at least one-and-a-half hour a day. In this way, there is more time for lunch (30 minutes), and PA and cultural activities (one hour);
- **Childcare staff** guide the lunch break. Although volunteers are still welcome to help, the lunch break is mainly guided by professionals;
- **Sport and cultural coaches** support childcare staff during the PA and cultural activities. External partners are active within the school environment;
- **Parents are actively involved** from the start of the project. They share their views on further development of the project and they volunteer during lunch breaks.

Two of the intervention schools implemented both a healthy school lunch and structured PA sessions during lunch break time (full HPSF schools). The other two intervention schools only implemented the structured PA sessions (partial HPSF schools). A detailed description of the study design, recruitment of participants and measurements can be found in Willeboordse et al. (32). Maastricht University is currently investigating the effects of HPSF on a broad range of effect measures (e.g., PA behaviour, BMI z-score, dietary behaviour). Although the project is still ongoing, interim analyses show promising effects. At two-year-follow-up, the study showed a significant decrease in BMI z-score of children in the HPSF schools as compared with children in control schools (33). Also, positive intervention effects on both dietary and PA behaviours were observed at two-year-follow-up (34).

These promising effects have led to an increased interest among other primary schools to implement changes fitting the HPSF initiative. One of these interested parties is educational board Prisma. Prisma comprises several childcare centres in Peel en Maas, a region in the northern part of Limburg. Both childcare and primary education for children aged 0-12 years are located in these childcare centres, meaning that children are looked after by the same people prior, during and after school time. The goal of Prisma is to ensure a healthy development for all children. A means to achieve this goal is to implement changes fitting the HPSF initiative. However, this is more complex than it seems to be, as the budget to implement changes is lower than in the original HPSF trial, and all childcare centres have their own unique context. Therefore, there is a need to investigate how HPSF can successfully be implemented in various, real-life school-settings. To maximise

implementation and sustainability, each childcare centre will need to put together their own unique set of changes and interventions which fit the context and the needs of all stakeholders involved (e.g., the school board, teachers, parents and children). All changes will fall in one of the four categories:

- Healthy and sustainable nutrition;
- Sufficient physical activity;
- Sufficient rest and relaxation;
- Collaboration and social involvement

To aid childcare centres in the development and implementation process and to study programme effectiveness, the 'Healthy Childcare Centre of the Future' (HCCF) project was initiated in cooperation with a broad range of partners. The first part of this project was to assess the needs of various stakeholders involved in the project, which was done via questionnaires and interviews with several stakeholders. Thanks to this needs assessment, childcare centres now have a better idea of the views of important stakeholders such as parents, children and teachers. The second part of the project comprises the actual implementation of HCCF within the Prisma childcare centres. Maastricht University plays an important role in HCCF. Researchers will play an advisory role and study the implementation process of HCCF at the childcare centres. Additionally, researchers will study the project's (cost-) effectiveness and compare its effects with the results from the HPSF quasi-experimental trial. In this way, effectiveness and sustainability can be investigated and factors influencing implementation in various contexts can be identified and evaluated.

### Conclusion

This observational study will show how and to what degree HCCF can effectively and sustainably be adapted and implemented in various contexts. In addition, barriers and facilitators of implementation will be identified and based on these factors, guidelines for widespread implementation will be formulated. Furthermore, the study will investigate the effects of HCCF on a range of outcome parameters among which health, lifestyle behaviours, and cost-effectiveness. The results of the effect-evaluation will be linked to the results of the process evaluation to identify implementation factors that influence effectiveness. In addition, the effects will be compared with the effects observed in the HPSF quasi-experimental trial to investigate the potential of HCCF to be implemented in a real-world setting.

## 1.1 Research questions

### Process evaluation:

- How and to what degree is HCCF adapted and implemented in various school contexts (e.g., changes in school's practices, rules and regulations)?
- What are barriers and facilitators of implementation of HCCF in various school contexts?
- How can these barriers and facilitators be anticipated upon to facilitate maximum widespread implementation of HCCF?
- What are the experiences of different stakeholders with HCCF?

### Effect evaluation:

- *Primary outcome:* At two-year follow-up, is there a difference in absolute BMI z-score between children from different childcare centres, which have been categorised based on their level of innovativeness and implementation?
- *Secondary outcomes:*
  - ➔ At two-year follow-up, is there a difference in waist/hip circumference between children from different childcare centres, which have been categorised based on their level of innovativeness and implementation?
  - ➔ At two-year follow-up, is there a difference in physical activity behaviours of children from different childcare centres, which have been categorised based on their level of innovativeness and implementation?

- ➔ At two-year follow-up, is there a difference in dietary behaviours of children from different childcare centres, which have been categorised based on their level of innovativeness and implementation?
  - ➔ At two-year follow-up, is there a difference in health markers of children from different childcare centres, which have been categorised based on their level of innovativeness and implementation?
- At two-year follow-up, is there a difference in school well-being of children from different childcare centres, which have been categorised based on their level of innovativeness and implementation?

**Cost-effectiveness evaluation:**

- Will HCCF be cost-effective?

**Comparison with original HPSF project:**

[figure not shown]
- Will the (cost-)effectiveness of HCCF be comparable with the (cost-)effectiveness of the original HPSF intervention?

## 2. METHODS

### 2.1 Study procedure/study design

The current study involves twelve childcare centres from the Prisma educational board, which are all located in Peel en Maas. The childcare centres are selected based on their expressed interest to participate in the project. The childcare centres are free to choose if, when and how they want to implement changes fitting HCCF. To study programme effectiveness, a non-randomised trial will be executed. Instead of true intervention and control childcare centres, after the project, the centres will be divided into groups based on their implementation phase. This division will be based on the Diffusion of Innovations Theory by Rogers (1995). According to Rogers, there are five types of adopters, which all have different adoption rates of a given innovation. From fast to slow adoption rate, these types of adopters are: innovators, early adopters, early majority, late majority and laggards. These adopters vary in adoption rate due to a difference in innovativeness; the degree to which an individual/organisation adopts a new idea (35). When looking at the Prisma childcare centres, it is likely that some childcare centres will adopt changes fitting HCCF earlier than others. Therefore, the different childcare centres can be categorised using Rogers' categories, which will facilitate comparison between the different childcare centres. It is expected that the childcare centres can be divided in three categories: innovators/early adopters, early/late majority and laggards.

The total study duration will be four years, of which roughly the first six months are preparation and the last year is evaluation. Therefore, data will be collected for approximately two years. Figure 1 provides an overview of the study.

## 2.2 Recruitment and selection of participants

### Study population

A closed design will be used, meaning that at baseline (T0), all children in study year four to six of the Prisma childcare centres will be invited to participate in the study. At T1, these children will be students in study year five to seven, and at T2 they will be in study year six to eight. Based on the amount of children enrolled in school year 2019/2020, approximately 685 children are eligible to participate in the study.

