### Inclusion- and exclusion criteria

In order to be eligible to participate in the study, a subject must meet all of the following criteria:

- Student of study year four to six at one of the participating childcare centres of Prisma;
- Informed consent signed by both caregivers.

No exclusion criteria are applicable as this is a real-life study and all students who meet the inclusion criteria will be included for participation in this study.

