### Number of anticipated participants

Childcare centres are free to choose if, when and to what degree they implement HCCF changes in their childcare centre. After data collection, the twelve childcare centres will be divided into three categories based on the Diffusion of Innovations theory (innovators/early adopters, early/late majority, laggards) (35). Because this categorisation occurs after data collection, it cannot yet be predicted which childcare centres will fall under which category. However, based on the childcare centres' intentions that have become clear during preliminary discussions about the project, three potential scenarios can be illustrated where childcare centres are categorised within the three groups. These scenarios are further illustrated in the light of three sample size calculations that allow for clustered sampling. For the calculations, the following website is used: <http://www.sample-size.net/means-effect-sizeclustered/> (36).

The sample size calculation was based on the primary outcome, i.e. to detect a difference in mean absolute BMI z-score between innovators/early adopters and laggards after two years intervention. The following general assumptions were used for the sample size calculation:

- Independent-samples t-test on difference in absolute BMI z-scores;
- Children are nested within schools;
- A significance level (alpha) of 0.05;
- A power of 80%;
- A dropout rate of 10%, as based on dropout rates observed by Bartelink et al.(33);
- An Intraclass Correlation Coefficient of 0.01, as based on Amorim et al. (37);
- Unequal cluster sizes with a relative efficiency of 90% (38);
- An average absolute BMI-z of 0.76 and an SD of 0.60 in the population (as no data was available for the population in Peel en Maas, these values were calculated over all children aged between 4 and 11 living in region Parkstad who visited the Youth Health Department in 2013).

### Scenario 1

- *Innovators/early adopters*: three childcare centres, number of participants (N1)=120
- *Laggards*: four childcare centres, number of participants (N3)=220
- Average size of each cluster (m): 50

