- With these assumptions we can demonstrate a Cohen's d of **0.369**, which means we can detect medium effect sizes on absolute BMI z-scores. A difference in mean absolute BMI z-score of **0.22** between innovators/early adopters and laggards can be detected. The detection of this difference is feasible in this population, as in a school-based longitudinal study with comparable intervention components, a mean difference between intervention and control group of -0.26 (CI 95%: 0.32, -0.21) BMI z-score was found (39).

### Scenario 2

- *Innovators/early adopters*: four childcare centres, number of participants (N1)=217
- *Laggards*: four childcare centres, number of participants (N3)=217
- Average size of each cluster (m): 55
- With these assumptions we can demonstrate a Cohen's d of **0.331**, which means we can detect medium effect sizes on absolute BMI z-scores. A difference in mean absolute BMI z-score of **0.20** between innovators/early adopters and laggards can be detected. The detection of this difference is feasible in this population, as in a school-based longitudinal study with comparable intervention components, a mean difference between intervention and control group of -0.26 (CI 95%: 0.32, -0.21) BMI z-score was found (39).

### Scenario 3

- *Innovators/early adopters*: four childcare centres, number of participants (N1)=217
- *Laggards*: five childcare centres, number of participants (N3)=303
- Average size of each cluster (m): 55
- With these assumptions we can demonstrate a Cohen's d of **0.314**, which means we can detect medium effect sizes on absolute BMI z-scores. A difference in mean absolute BMI z-score of **0.19** between innovators/early adopters and laggards can be detected. The detection of this difference is feasible in this population, as in a school-based longitudinal study with comparable intervention components, a mean difference between intervention and control group of -0.26 (CI 95%: 0.32, -0.21) BMI z-score was found (39).

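### The detectable differences of 0.22, 0.20 and 0.19 are too favourable: the listed numbers do not deliver them once the plan's own dropout and relative efficiency are applied, and nothing is allowed for non-consent

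*Combined protocol and SAP*

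**What the plan says.** Section 2.1 gives the number of centres: "The current study involves twelve childcare centres from the Prisma educational board". Section 2.2, Study population, gives the pool, counted from 2019/2020 enrolment: "approximately 685 children are eligible to participate in the study". The inclusion criteria then require "Informed consent signed by both caregivers".

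The section on anticipated participants compares innovators/early adopters with laggards. Its listed assumptions include "Independent-samples t-test on difference in absolute BMI z-scores", "A significance level (alpha) of 0.05", 80% power, "A dropout rate of 10" per cent, an intraclass correlation of 0.01, a relative efficiency of 90% for unequal clusters and an SD of 0.60. No participation or consent rate is listed.

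The scenarios are:

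- Scenario 1: 120 children in three centres against 220 in four, cluster size 50; d = 0.369, difference 0.22.
- Scenario 2: 217 in four against 217 in four, cluster size 55; d = 0.331, difference 0.20.
- Scenario 3: 217 in four against "five childcare centres, number of participants (N3)=303", cluster size 55; d = 0.314, difference 0.19.

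Each scenario is called feasible by comparison with a reported difference of -0.26 in another school-based study.

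**The concern.** There are two gaps. First, the stated differences do not appear to include the dropout and unequal-cluster losses that the same section lists. Second, the pool of 685 is counted from enrolment, before anyone has consented, while the scenario figures are labelled participants and in two scenarios are about as large per centre as average enrolment. Dropout does not cover non-consent, because it acts only on children already in the study.

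The design is closed and every child in the three study years is invited, so a shortfall cannot be made up by recruiting more. If the stated differences are too small, a null primary result will be read against a sensitivity that the study did not have.

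**Working it through.** **Inputs.** N1, N3, cluster size m, ICC 0.01, SD 0.60, alpha 0.05, power 80%, dropout 10% and relative efficiency (RE) 90%, all from section 2.2. The plan does not state whether the test is one- or two-sided; two-sided is assumed, because the primary research question asks whether there is a difference, without direction.

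**Formula.** SE = sqrt[(DE/RE) × (1/n1 + 1/n3)], with DE = 1 + (m − 1) × 0.01. Detectable d = (1.960 + 0.842) × SE. Detectable difference = 0.60 × d. Power at the stated d = Φ(d/SE − 1.96).

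**Step 1: reproduce the plan.** With neither dropout nor RE applied, d = 0.388, 0.334 and 0.309, against the stated 0.369, 0.331 and 0.314. A noncentral-t version gives 0.390, 0.335 and 0.310. Scenarios 2 and 3 are then close; scenario 1 would need about 11% more children than listed. None of the variants tried (dropout only, RE only, dividing instead of multiplying, equal allocation, one-sided) reproduces all three figures.

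**Step 2: apply the plan's own dropout and RE, full participation.** Dropout multiplies both N and m by 0.9.

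- Scenario 1: n = 108 and 198, m = 45, DE = 1.44. SE = sqrt[(1.44/0.9) × (1/108 + 1/198)] = 0.1513. d = 0.424, difference 0.254. Power = Φ(0.369/0.1513 − 1.96) = 68%.
- Scenario 2: n = 195.3 and 195.3, m = 49.5, DE = 1.485. SE = 0.1300, d = 0.364, difference 0.219, power 72%.
- Scenario 3: n = 195.3 and 272.7, m = 49.5, DE = 1.485. SE = 0.1204, d = 0.337, difference 0.202, power 74%.

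If m is not reduced for dropout, the results are slightly worse: 0.26, 0.22 and 0.21, with power of 67%, 71% and 73%.

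**Step 3: compare the counts with enrolment.** 685/12 = 57.1 enrolled children per centre.

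| Scenario | Listed | Centres | Per centre | Share of 57.1 |
|---|---|---|---|---|
| 1 | 340 | 7 | 48.6 | 85% |
| 2 | 434 | 8 | 54.3 | 95% |
| 3 | 520 | 9 | 57.8 | 101% |

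One bound needs no assumption about centre size: scenario 3 requires at least 520/685 = 76% participation, even if the other three centres had no eligible child. At 80% participation its nine centres would need 520/0.8 = 650 enrolled children (72 each), leaving 35 for the other three (about 12 each). At 90% they would need 578 (64 each), leaving 107 (about 36 each). So with centres near the average size, scenario 3 implies almost full participation.

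**Step 4: add participation p.** The documents give no rate, so 60–80% is an assumption shown as a range. N and m are multiplied by p as well as 0.9.

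| p | Detectable difference, scenarios 1 / 2 / 3 | Power at stated d |
|---|---|---|
| 100% | 0.254 / 0.219 / 0.202 | 68 / 72 / 74% |
| 80% | 0.275 / 0.236 / 0.219 | 62 / 65 / 68% |
| 60% | 0.307 / 0.263 / 0.243 | 52 / 56 / 58% |

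**Step 5: split the loss.** Of the fall from 80% power, 12, 8 and 6 points are already present at full participation (80 − 68, 80 − 72, 80 − 74). Participation adds about 6–7 points at 80% and about 16 points at 60%.

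**The case against.** The strongest reply is that the scenario figures may be net numbers. They are labelled participants, and nothing says that they are counted before dropout. If they are already net of dropout, step 2 deducts it twice. That stands as an ambiguity, but it does not rescue the figures. RE alone (n and m as listed, variance divided by 0.9) gives differences of 0.245, 0.211 and 0.196, still above those stated. The recruits needed would rise to 340/0.9 = 378, 434/0.9 = 482 and 520/0.9 = 578, which is 95%, 106% and 113% of enrolment at average centre size.

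Second, sidedness is not stated. A one-sided test with both adjustments gives d of about 0.384, 0.330 and 0.306 with m as listed, which is close to or below the stated values in scenarios 2 and 3. The finding therefore rests on a two-sided reading, which fits the undirected research question.

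Third, a reader might infer that the listed numbers are the eligible headcount and that the plan assumes two signatures for every child. The documents do not show this. They give no enrolment per centre, clusters are expected to be unequal, the scenarios cover only two of the three groups, and scenario 1 sits at 85% of average, which could reflect smaller centres or some non-participation.

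Fourth, the t-test power is not the power of the planned analysis, a mixed model with repeated measures and baseline covariates that may gain precision. That is fair. It limits what can be said about the final analysis, but the sample size section should still be correct on its own terms.

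**Conclusion.** The point holds in a limited form. On a two-sided test, the stated differences of 0.22, 0.20 and 0.19 become about 0.25, 0.22 and 0.20 once the plan's own dropout and RE are applied to the listed numbers, with power of 68–74% instead of 80%. Separately, the plan has no term for non-consent although both caregivers must sign, and scenarios 2 and 3 leave almost no room for it if centres are near average size. The only bound free of that assumption is 76% for scenario 3.

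It would be tempting to blame the whole shortfall on non-consent. The figures do not support that: part of it exists at full participation, and the size of the remainder depends on a rate that the documents do not give.

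Nor does the feasibility argument against 0.26 collapse everywhere. With dropout and RE applied, scenario 1 is just inside it at full participation (0.254) and outside it at 80% (0.275). Scenario 2 reaches it at about 60% (0.263). Scenario 3 stays inside it across the assumed range (0.243 at 60%).

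**What to change.** In section 2.2, under the number of anticipated participants:

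1. State whether N1 and N3 are before or after consent and before or after dropout, and whether the test is two-sided.
2. Give enrolment per centre and multiply it by an expected two-caregiver consent rate with its source. If no rate can be justified, show a range.
3. Apply the stated 10% dropout and 90% relative efficiency explicitly.
4. Restate N1, N3, m, d and the detectable difference for each scenario, and revisit the comparison with 0.26 scenario by scenario.

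This costs wording and a short recalculation. It does not call for enrolling more children, since all eligible children are already invited. The restated figures will be less favourable than the present ones.
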